### 6.3 Randomization and Blinding

This study used randomization and masking as two of the cardinal principles of clinical trials to minimize bias.

*Randomization.* Participants were randomized after all screening assessments were completed and the investigator verified that eligibility criteria were met. Eligible participants were randomized to MMF+PFD or MMF+Plac in a 1:1 manner, stratified by clinical site (pooled into 4 groups) and prior MMF exposure (naïve, >0 to  $\leq$ 3 months, and >3 months to  $\leq$ 6 months). Randomization to the different strata were to be capped if necessary to maintain at least 50% of randomized subjects within the treatment naïve strata (no prior therapy with MMF or DMARD) in order to maintain adequate power. The DCC prepared the randomization schedule, using computer-generated block randomization with the block size(s) known only by the DCC. A secure web-based application was built for use by the coordinators to enter participant information (e.g., participant ID, stratification factor) and to obtain the randomization number. The information was printed and sent and/or emailed directly to the site pharmacists. Participants who withdrew from the study prior to completion of the treatment period were not replaced.

*Blinding.* This is a double-blind study. The study staff (except for select staff at the DCC and Research Pharmacists) and the participant were blinded to the treatment assignment.

## 6.4 Study Assessments

The Schedule of Activities details the study procedures:

	Screen		Randomized Double-blind Phase																					Exit visit*
	S1	S2	V1	V2	V3	V4	V5	V6	V7	V8	V9	V10	V11	V12	V13	V14	V15	V16	V17	V18	V19	V20	V21	
Visit #	Sc-1	Sc-2	0	0.5 (14 days) ±7d	1 (28 days) ±7d	1.5 (42 days) ±7d	2 (56 days) ±10d	3 (84 days) ±10d	4 (112 days) ±10d	5 (140 days) ±10d	6 (168 days) ±10d	7 (196 days) ±10d	8 (224 days) ±10d	9 (252 days) ±10d	10 (280 days) ±10d	11 (308 days) ±10d	12 (336 days) ±10d	13 (364 days) ±10d	14 (392 days) ±14d	15 (420 days) ±10d	16 (448 days) ±10d	17 (476 days) ±10d	18 (504 days) ±14d	V22
Month on Study (Month = 28 days)																							Month 19 (532 days) ±10d	
Phone contact				X	X							X	X		X	X		X	X		X	X	X	X
On-Site Visit	X	X	X		X		X	X	X	X	X			X			X			X			X	
Complete H&P	X																							
F/u SSc-H&P			X		X		X	X	X	X	X			X							X		X	
Vital signs	X		X		X		X	X	X	X	X			X			X			X		X	X	
mRSS			X				X			X			X			X			X			X		
Study Consent	X																							
Adverse events			X	X	X	X	X	X	X	X	X	X	X	X	X	X	X	X	X	X	X	X	X	
Concomitant Medications	X		X	X	X	X	X	X	X	X	X	X	X	X	X	X	X	X	X	X	X	X	X	
Dispense meds			X		X		X	X	X	X	X			X			X			X				
Drug reconciliation			X		X		X	X	X	X	X			X			X			X		X		
Mahler BDI/TDI			X				X			X			X			X			X			X		
SGRQ			X				X			X			X			X			X			X		
SHAQ, PROMIS-29, UCLA SCTC GIT, CRISS, LCQ, Global Assessments	UCLA SCTC GIT		X (except CRISS)								X													X
LABS:																								
- CBC, diff, plat	X				X		X	X	X	X	X			X			X			X		X	X	
- Metabolic/liver	X				X		X	X	X	X	X			X			X			X		X	X	
- Serum Preg +	X																							
- Urine Preg +			X		X		X	X	X	X	X			X			X			X		X	X	
HRCT		X																						X
Spiro/DLCO	X		X ‡				X			X			X			X			X		X		X	
Biorepository			X																X					X

‡Screen and Baseline FVC value must be within an absolute difference in percent-predicted of 10% - may repeat within 7 days if not and proceed to enroll if criteria met

\*For women of childbearing potential, initial serum pregnancy testing will be carried out with subsequent urine testing at each visit using test kits provided by the study.

\*\*Exit visit will also be carried out within 30 days (±10d) of early termination/withdrawal from the protocol. All subjects who terminate/withdraw early will be encouraged to return for the outcome assessments as detailed above for the 12 month (V15) and 18 month (V21) visits.

\*\*Refer to Protocol Section 17.0 (EMERGENCY DISASTER/ PANDEMIC MANAGEMENT PLAN) for allowed adjustments in the event of a disaster/pandemic that disrupts patient or institutional access.

### 6.4.1 Primary Efficacy Assessment

The primary endpoint is change from baseline in the mean forced vital capacity, measured as the percentage of the age-, height-, gender- and race-adjusted predicted value (FVC-%) over the course of the 18-month treatment period, as reported quarterly (i.e., months 3, 6, 9, 12, 15 and 18.) The change from baseline at each time point is calculated as FVC-% at x months minus FVC-% at baseline. The calculation of percent predicted FVC is based on equations from Hankinson (see table below).

Result name	Formula
Age	(Date of PFT – Date of birth)/365.25 
 
For screening, rescreening, baseline, and repeat baseline visits, round down to the nearest integer. This is used for eligibility determination.
 
For all efficacy analyses, use the fractional age (i.e., do not round) for all values including baseline.
 

FVC	Where H = height in centimeters and Age = Age defines as above
Predicted (Reference)	Caucasian 
Males≥20: <math>FVC(L) = 0.00018642*H^2 + 0.00064*Age - 0.000269*Age^2 - 0.1933</math>
 
Males<20: <math>FVC(L) = 0.00018642*H^2 - 0.20415*Age + 0.010133*Age^2 - 0.2584</math>
 
Females≥18: <math>FVC(L) = 0.00014815*H^2 + 0.01870*Age - 0.000382*Age^2 - 0.3560</math>

	African-American 
Males≥20: <math>FVC(L) = 0.00016643*H^2 - 0.01821*Age - 0.1517</math>
 
Males<20: <math>FVC(L) = 0.00016643*H^2 - 0.15497*Age + 0.007701*Age^2 - 0.4971</math>
 
Females≥18: <math>FVC(L) = 0.00013606*H^2 + 0.00536*Age - 0.000265*Age^2 - 0.3039</math>

FVC Percent Predicted	NOTE 1: Those subjects who indicate that they are both African American and Mexican-American or Hispanic will use the African American reference equations; those subjects who indicate that they are both Caucasian and Mexican-American or Hispanic will use the Caucasian reference equations. NOTE 2: Those subjects who indicate that they are Asian will use 0.88x the Caucasian values. NOTE 3: If Race is "Unknown or Not Reported", then use Caucasian values.

### 6.4.2 Secondary Efficacy Assessments

#### 6.4.2.1 FVC

FVC is measured in milliliters at baseline and months 3, 6, 9, 12, 15 and 18.

#### 6.4.2.2 DLCOHb-%

Single-breath diffusing capacity for carbon monoxide (DLCO), calculated as a percent of the age-, height-, gender-, and hemoglobin-adjusted predicted value (DLCOHb-%). It is assessed at baseline, and months 3, 6, 9, 12, 15, and 18. The calculation of predicted DLCO is based on equations from Neas and Schwartz and the calculation of hemoglobin-adjusted predicted DLCO is based on equations from Cotes (see table below).

Result name	Formula
Age	
(Date of PFT – Date of birth)/365.25
 
 
1. For screening, rescreening, baseline, and repeat baseline visits, round down to the nearest integer. This is used for eligibility determination.
 
2. For all efficacy analyses, use the fractional age (i.e., do not round) for all values including baseline.
 

DLCO Predicted (Reference)	
Where H = height in centimeters and Age = Age defined as above.
 
Caucasians
 
Males: <math>DLCO \text{ (mL/min/mmHg)} = 0.291*H - 0.208*Age - 7.86</math>
 
Females: <math>DLCO \text{ (mL/min/mmHg)} = 0.255*H - 0.097*Age - 12.40</math>
 
African-Americans
 
Males: <math>DLCO \text{ (mL/min/mmHg)} = 0.323*H - 0.198*Age - 16.46</math>
 
Females: <math>DLCO \text{ (mL/min/mmHg)} = 0.136*H - 0.108*Age + 4.77</math>
 
NOTE 1: For minorities other than African-Americans, the prediction equations for Caucasians will be used.
 
NOTE 2: If "Unknown or Not Reported", then use Caucasian values.

DLCO, Adjustment for hemoglobin	
Men: <math>DLCO_{Hgb\_adjusted\_reference} = DLCO_{reference} \times (1.7 \times Hgb) / (10.22 + Hgb)</math>
 
Women: <math>DLCO_{Hgb\_adjusted\_reference} = DLCO_{reference} \times (1.7 \times Hgb) / (9.38 + Hgb)</math>
 
NOTE 1: The hemoglobin will be reported from the study blood draw closest to the DLCO measurement. Ideally this will be within 4 weeks.

DLCO Percent Predicted (Adjusted for Hgb)	
<math>(DLCO \text{ Observed} / DLCO_{Hgb\_adjusted \text{ reference}}) * 100</math>

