Study Duration:	Approximately 4 years total study duration, sub-divided into the following components: 
 24 month enrollment period 18-month randomized, double-blind treatment period per patient 1 month follow-up period after completion of drug therapy 6 month primary analysis period
Participant Duration:	20-22 month subject participation period made up of the following components:

	
 - screening = 1-3 months - randomized, double-blind treatment period = 18 months - final follow-up period after completion of drug therapy = 1 month
Inclusion Criteria:	
 1. Age \geq18 yrs 2. Scleroderma as determined by the 2013 ACR/EULAR classification criteria. 3. Grade \geq2 on the Magnitude of Task component of the Mahler Modified Dyspnea Index (Becomes short of breath with moderate or average tasks such as walking up a gradual hill, climbing less than three flights of stairs, or carrying a light load on the level.) 4. FVC-% of \leq85% at screening. 5. Onset of the first non-Raynaud manifestation of SSc within the prior 84 months. 6. Presence of any GGO on thoracic HRCT 7. Repeat FVC-% at the baseline visit within 10% of the FVC-% value measured at screening. If these criteria are not met, a repeat FVC-% may be obtained within 7 days and the subject may qualify for randomization if the repeat FVC-% agrees within 10% of the FVC-% obtained at screening.

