7.1.1.2 **Single-breath diffusing capacity for carbon monoxide (DLCO) and DLCO adjusted for hemoglobin (DLCOHb)**. DLCO measurements will be performed in accordance with published ATS/ERS guidelines using equipment and testing techniques that meet ATS/ERS requirements (33). At least 2 acceptable tests that meet repeatability criteria (33) will be performed and the mean DLCO value (uncorrected for Hgb) from acceptable measurements reported. Other reported values will include the inspired vital capacity, which must be within 10% of the expiratory Vital Capacity, and the alveolar volume. DLCO will then be corrected for hemoglobin that will be measured at the corresponding study visit as part of the blood monitoring and reported as DLCOHb. DLCO and DLCOHb will be expressed both as measured values and as a percentage of gender-specific predicted values (DLCO-% and DLCOHb-%) using the regression equations of Neas (37). The race-specific equations of Neas et al. (53) will also be used for calculation of the predicted values of DLCO for African-Americans. DLCO measurements will be performed at entry (screening), just prior to initiation of study medication (baseline) and every 3 months for the entire 18 months of the study.

In the event that a participant has already completed DLCO testing within 30 days of the Screening Visit #1 and the testing meets all eligibility criteria, it may be used in lieu of repeating the DLCO measurements at Screening Visit #1. In order to be considered eligible, the testing must have been performed at the same facility that will be used during the

study, the full DLCO data set must be available for review and it must pass a Quality Assurance review by the Pulmonary Function Core at UCLA.

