7.1.2 Standard of Care Study Procedures

7.1.2.1 **Complete medical history and physical examination.** A complete medical history and physical exam covering details related to the patient's history of scleroderma, their entire medical history with a review of systems, and their current physical findings will be

performed during the initial screening visit and at 12 months. This will include a review of pertinent medical records provided by the patient and/or their referring physicians.

7.1.2.2 **Focused Interval history and examination.** A review of current symptoms, medications, physical findings and any changes noted by the patient or a physician since a prior visit will be performed at baseline, monthly for the first 6 months and then every 3 months.

7.1.2.3 **Vital signs.** Vital signs will include: pulse, blood pressure, respiratory rate, temperature (°C), weight (kg), and SpO₂ by pulse oximetry will be performed at initial screening, baseline, monthly for the first 6 months and then every 3 months. Height (cm) will only be done at screening.

7.1.2.4 **Toxicity Monitoring with Blood Tests.** A comprehensive set of laboratory results performed on a current blood sample to evaluate any toxicity or adverse events associated with Scleroderma or its treatment with the study drugs. Blood tests will include: comprehensive metabolic panel (to include serum electrolytes, BUN, Cr, glucose, albumin, ALT, AST, alkaline phosphatase, bilirubin, total protein) and a complete blood count with differential (to include WBC, Hgb, hematocrit, platelet count, and cellular differential count including absolute neutrophil count). Monitoring will occur at initial screening, monthly for the first 6 months and then every 3 months.

In the event that a participant has had all required laboratory tests completed within 30 days of the Screening Visit #1, the results may substitute for the official screening laboratory tests.

7.1.2.5 **Pregnancy Testing.** An initial serum pregnancy test at screening and subsequent monitoring with urine pregnancy testing to be performed on all female participants of child-bearing potential at baseline, monthly for the first 6 months and then every 3 months.

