7.2.1 Screening Visits (Study Day -90 through 0; Screening Visit #1&2)

In order to be eligible for randomization, patients must proceed through a series of screening steps. At Screening Visit #1, a preliminary evaluation is performed and if eligibility criteria are met the patient will proceed to the screening HRCT scan (Screening Visit #2) to assess for the presence of any ground glass opacity and to exclude concurrent findings of concern that may require additional evaluation or exclude the patient from further participation. If all inclusion and exclusion criteria are met, the patient will proceed to the baseline evaluation where a final check of pulmonary function and pregnancy testing is required to meet randomization criteria:

7.2.1.1 **Screening Visit #1.** (preferably within 60 d, but no earlier than 90 d prior to randomization)

- Patient provides written informed consent and research HIPAA authorization prior to any evaluation or testing.

- b. A review of existing medical records and tests, provided by the patient or referring physician, is performed to document the history of scleroderma and general medical history.
- c. Vital signs obtained.
- d. The patient undergoes a complete medical history and physical examination.
- e. Review of concomitant medications including all medications taken within past 3 months and any prior use of medications detailed in Section 7.5.1 (Prohibited Medications & Treatments with Potential Disease Modifying Effects).
- f. Pulmonary function testing for spirometry and diffusing capacity will be completed unless acceptable testing has been completed within 30 days of the screening visit and approved in advance by the Pulmonary Function Core at UCLA.
- g. A limited subset of the UCLA SCTC GIT questionnaire (including only Questions #1-8) is completed by the participant
- h. The patient has blood drawn for monitoring blood tests and serum pregnancy test (if applicable).

7.2.1.2 **Screening Visit #2.** (may not be completed until results from screening visit #1 confirm potential eligibility, must be completed within 60 days of randomization)

- a) Thoracic HRCT with visual review for the presence of entry and exclusion criteria and with Quantitative Image Analysis

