7.2.2 Enrollment/Baseline Visit (Study Day 0; Visit #1)

Subjects who meet all defined inclusion and exclusion criteria (up to this point) will be asked to return for the baseline visit. This will preferably occur within 60 days of their initial screening evaluation, but must occur within 90 days of their initial evaluation. For subjects who have not met study enrollment criteria, their participation will end and they will not proceed. The following studies will take place at the baseline visit.

- a) A focused interval history and examination will be performed.
- b) Vital signs obtained.
- c) Review of concomitant medications
- d) Pulmonary function testing for spirometry and diffusing capacity will be completed.
- e) Urine pregnancy test performed (if indicated)
- f) Patient Reported Outcomes (PROs) in the form of patient responses to standardized patient questionnaires (SGRQ; SHAQ; PROMIS-29; UCLA SCTC GIT; LCQ).
- g) Complete the Mahler Baseline Dyspnea Index.
- h) An assessment of skin thickness and function scores (mRSS)
- i) Patient and Physician Global Assessments (no transition questions)
- j) Blood collection for the Biological Specimen Repository

If the repeat FVC-% fails to be within 10% of the value obtained at screening or is not > 45% and ≤ 85%, the subject will be offered one opportunity to repeat testing within 7 days. If they choose not to repeat testing or if the repeat testing remains outside of the required range, their participation in the study will end.

If the subject meets the repeat FVC-% inclusion criteria, and assuming that pregnancy testing is negative if required, the site coordinator will complete the online eligibility case report form and login to the electronic web-based randomization application to randomize the participant.

Once randomization has occurred, the UCLA Pharmacy Core or the designated site Pharmacy, will confirm the drug and bottle assignment. In conjunction with a prescription signed by the Clinical Site

investigator, study drugs will be dispensed according to established protocol. Randomization will occur via the Data Coordinating Center and result in a notification of study assignment group to the UCLA Pharmacy Core and the Site Pharmacy. Study drug (PFD/Plac) will be released in a double-blinded manner and neither the study investigators or staff, or the patient, will know the treatment assignment.

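### No hemoglobin is scheduled at baseline, and the SAP's closest-draw rule lets baseline DLCOHb-% use the month-1 on-treatment value

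*SAP*

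**What the plan says.** SAP 6.4.2.2 gives one hemoglobin rule for all DLCOHb-% values, baseline included: "The hemoglobin will be reported from the study blood draw closest to the DLCO measurement. Ideally this will be within 4 weeks". It looks in both directions in time and does not treat baseline separately.

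Protocol 7.1.1.2 says something different: "DLCO will then be corrected for hemoglobin that will be measured at the corresponding study visit as part of the blood monitoring". That cannot be done at baseline. Protocol 7.1.2.4 sets the timing of the blood counts: "Monitoring will occur at initial screening, monthly for the first 6 months and then every 3 months". The baseline list in Protocol 7.2.2 has a urine pregnancy test and "Blood collection for the Biological Specimen Repository", but no blood count. The visit tables in both documents agree.

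The draws on either side of baseline are:

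- **Screening Visit 1.** Protocol 7.2.1.1 places it "preferably within 60 d, but no earlier than 90 d prior to randomization", and the Participant Duration entry in the Protocol Summary plans "screening = 1-3 months". For outside tests done within 30 days of that visit, Protocol 7.1.2.4 adds that "the results may substitute for the official screening laboratory tests".
- **Visit 3 (month 1).** Day 28, with a window of 7 days either side.

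Under SAP 10.2.2, item 1, the baseline value is subtracted to form the change score and is also a model covariate.

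**The concern.** At months 3 to 18 a blood count is scheduled at every DLCO visit, so the rule does no harm there. It fails only at baseline, the value on which every change score depends. The baseline DLCO is measured before study drug but may be corrected with a hemoglobin drawn about four weeks into treatment. If hemoglobin has moved by then, the baseline is wrong by an amount related to treatment, and the error carries into every visit's change and into the covariate. A baseline covariate should not contain post-randomisation information. The SAP itself calls DLCOHb-% the most variable of the lung function tests (section 14, item c), and its primary model is indexed to 51 participants (10.1), so avoidable error matters.

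**Working it through.** The plan states no figure to reproduce on this point. Two questions can be checked.

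**1. When is the month-1 draw the closest?**

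Let G be the days from the screening draw to baseline and V the days from baseline to Visit 3. The month-1 draw is chosen when V < G. With Visit 3 on its nominal day, that means any G above 28.

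The documents cap G at 90 days (preferably 60) for a draw at Screening Visit 1. They give no binding minimum and no distribution. I therefore assume G uniform on (a, b) and V uniform on 21-35.

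- If a ≤ 21 and b ≥ 35, the share is (b − 28)/(b − a).
- If a = 28, the share is 1 − 1.75/(b − 28), because the part of the range below 35 loses 24.5/14 = 1.75.
- For 7-28 days, the share is 1.75/21.

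| Assumed G (days) | Arithmetic | Share using month-1 draw |
|---|---|---|
| 28-90 | 1 − 1.75/62 | 97% |
| 28-60 | 1 − 1.75/32 | 95% |
| 0-90 | 62/90 | 69% |
| 0-60 | 32/60 | 53% |
| 7-42 | 14/35 | 40% |
| 7-28 | 1.75/21 | 8% |

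Simulation with the same assumptions gave the same shares. The first two rows fit the planned one to three months of screening. The last row needs sites to finish screening within four weeks, which the schedule allows. Substituted outside labs lengthen G and raise every share.

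**2. How far does the baseline move?**

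SAP 6.4.2.2 multiplies the reference DLCO by f(Hgb) = 1.7·Hgb/(c + Hgb), with c = 9.38 for women and 10.22 for men. Replacing a pre-dose value h0 with a month-1 value h1 moves a baseline of D points by D × [f(h0)/f(h1) − 1].

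Example, a woman going from 12.5 to 11.5 g/dl: f(12.5) = 21.25/21.88 = 0.9712; f(11.5) = 19.55/20.88 = 0.9363; ratio 1.0373. The shift is 1.86 points at D = 50 and 2.24 at D = 60.

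| Fall in Hgb (g/dl) | Woman, from 12.5 | Woman, from 13.4 | Man, from 14.0 |
|---|---|---|---|
| 0.25 | 0.44-0.52 | 0.39-0.47 | 0.38-0.46 |
| 0.5 | 0.89-1.07 | 0.80-0.96 | 0.78-0.94 |
| 1 | 1.86-2.24 | 1.66-1.99 | 1.62-1.95 |

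Each range runs from D = 50 to D = 60. The D values, the starting hemoglobins and the falls are all assumed; the documents give none of them for month 1. A fall raises the baseline percentage and so lowers every later change by the same amount.

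**The case against.** The strongest reply is that a pre-dose value must already exist. Baseline DLCOHb-% below 25% is an exclusion (SAP 6.2.2, item 4), so it has to be calculated before randomisation, when only the screening hemoglobin is available. The SAP does not say that hemoglobin is chosen again later. This narrows the point but does not remove it. The same SAP table says eligibility uses age rounded down while efficacy analyses use fractional age, baseline included. Baseline percent-predicted is therefore recomputed for efficacy, when the month-1 draw is on file, and the hemoglobin rule read literally selects it.

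Four stronger readings are tempting, and the documents do not support them:

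- **That most participants are affected, as a fact.** This is an inference from the planned screening length. No minimum gap binds.
- **That everyone with a 30-day washout is affected.** With a 30-day gap and Visit 3 on days 31-35, the screening draw is closer. A drug stopped before screening also needs no 30-day gap after it.
- **That hemoglobin is known to fall by month 1.** The 12% anaemia figure for MMF (Protocol 2.3.1.1.4) covers a two-year course. At day 28 an MMF-naïve participant has had only the first titration step (Protocol 6.1.4.1).
- **That the treatment comparison is biased.** Both arms receive MMF, so its effect cancels on average. Bias needs a pirfenidone effect on hemoglobin by day 28. Anaemia is not in the tabulated pirfenidone reactions (Protocol 2.3.1.2.4). The SSc-ILD tolerability study, in which 63.5% also took MMF, found no clinically relevant laboratory abnormality (Protocol 2.1.6 and 2.3.1.2.5).

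It is also fair to say that a baseline shift is the same at every visit, so it leaves the treatment-by-month term, the parameter named in SAP 10.1, unmoved. It can move the level of the adjusted mean changes, which SAP 10.2.2 reports and plots by arm and month.

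**Conclusion.** The point holds as a defect in the definition of one secondary endpoint. No hemoglobin is scheduled at baseline, the SAP rule has no pre-dose limit, and the Protocol's same-visit rule cannot be met there. Baseline DLCOHb-% can therefore use on-treatment hemoglobin, and usually would if screening takes the planned one to three months.

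Per affected participant the shift is about 0.4-0.5 points for a 0.25 g/dl fall and 1.6-2.2 points for 1 g/dl, under the assumed values above. A shift common to both arms distorts the within-arm mean changes and adds error. Between-arm bias is possible but has no figure behind it in the documents. The primary endpoint is not touched. The rule should be corrected, because it puts post-randomisation data into a baseline covariate when a pre-dose value is already collected.

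**What to change.** In SAP 6.4.2.2, define baseline DLCOHb-% with the last hemoglobin drawn before the first dose of study drug, and say that an accepted substitute screening result counts. Keep the closest-draw rule for post-baseline visits, where a same-visit count is scheduled. Reconcile this with Protocol 7.1.1.2, which asks for a same-visit hemoglobin that the schedule does not supply at baseline.

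The change is a line of text and a line of code, and needs no new data. Its cost is age. The pre-dose hemoglobin may be up to 90 days old, or about 120 (90 + 30) where outside labs stand in for the screening labs, so it can miss the SAP's four-week aim. If a washout starts after screening, the screening sample also reflects the earlier drug, while the baseline DLCO follows the washout. That staleness adds some error of its own, but the error arises before randomisation and cannot depend on assigned treatment.
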